### 4. ENDPOINTS

As Cohort 1 includes healthy volunteers no efficacy data will be collected. Though some efficacy assessments are included for Cohort 2 the data will only be listed and no formal comparisons will be made between the treatment groups. Consequently efficacy endpoints will only be assessed for Cohort 3.

#### 4.1. PRIMARY EFFICACY ENDPOINT

The primary efficacy endpoint for Cohort 3 is the percentage change from baseline to Week 2 in the EASI score.

The EASI is a validated tool used to measure the severity and extent of atopic eczema (refer to Protocol Appendix 11 – EASI for descriptions of the ratings and the algorithm used to calculate the EASI score). The total score incorporates the extent of body regions affected and the intensity of a representative area of eczema. The approximate percentages affected by eczema are calculated for each region. A higher score indicates more severe disease.

EASI is assessed at all visits for Cohorts 2 and 3, and must be  $\geq 9$  and  $\leq 48$  at screening and  $\geq 12$  and  $\leq 48$  on Day 1 for the patient to be eligible for inclusion in the study.

#### 4.2. SECONDARY EFFICACY ENDPOINTS

The secondary efficacy endpoints for Cohort 3 are:

#### EASI-50

EASI-50 response (yes/no). This is defined as a  $\geq$ 50% reduction from baseline in EASI score at Week 2.

#### **EASI-75**

EASI-75 response (yes/no). This is defined as a  $\geq$ 75% reduction from baseline in EASI score at Week 2.

#### **EASI Components**

A score for the EASI components (erythema [E], oedema/papulation [O], excoriation [X] and lichenification [L]) will be calculated across the body regions in a similar way to the calculation of the EASI total score. For example:

Erythema= $[0.1xE_{head}XExtent_{head}]$ +  $[0.2xE_{arms}XExtent_{arms}]$ +  $[0.3xE_{trunk}XExtent_{trunk}]$ + $[0.4xE_{legs}XExtent_{legs}]$ 

The secondary endpoints associated with Cohort 3 are percentage change from baseline for each of the EASI components (erythema, oedema/papulation, excoriation and lichenification).

### **Investigator Global Assessment (IGA)**

An overall assessment of the severity of AD will be made, by the investigator, using the IGA at

SAP Version v2.0 Page 17 of 43

Date: 16th March 2017

each visit for Cohorts 2 and 3. IGA scores take values on a 5-point scale from 0-4, where 0=clear to 4=severe disease. At screening and Day 1 IGA must be  $\geq$  3 for the subject to be eligible.

The following secondary endpoints will be assessed for IGA for Cohort 3:

- A subject will be considered as having IGA success if they achieve a score of 'Clear' or 'Almost clear'; note, as subjects require a score of ≥ 3 to enter the study they must have a reduction of ≥ 2 from baseline to achieve success
- A subject will be considered as having an IGA response if they achieve a score of 'Clear' or 'Almost clear', or a reduction of ≥ 2 from baseline

### **Numerical Rating Scale (NRS)**

The Pruritus NRS is an assessment tool that will be used to assess the subject's worst itch as a result of AD in the previous 24 hours. Subjects in Cohort 3 will be required to complete the Ziarco Itch questionnaire at each visit from baseline to follow-up. They will be asked the question "On a scale of 0 (No Itching) to 10 (Itching as bad as you can imagine), please rate the WORST itching that you felt over the last 24 hours."

To determine the duration of itching, subjects will be asked "Over the last 24 hours approximately how many hours, if any, did you itch?". To determine the level of sleep disturbance due to itching, subjects will be asked "On a scale of 0 (No sleep disturbance) to 10 (Awake all night), please rate how much your sleep was disturbed by itch last night".

Subjects will be asked to rate their itch over the last 24 hours using a verbal rating score (VRS). This is a list of adjectives describing different levels of symptom intensity - no itch, mild, moderate and severe.

The secondary endpoints for Cohort 3 associated with NRS are:

- Change from baseline in the NRS for pruritus (worst itch) at Week 2
- Average change from baseline in NRS for pruritus (worst itch) over Days 8, 10 and 15
- Change from baseline in the NRS for sleep disturbance at Week 2
- Change from baseline in total duration of itching at Week 2
- Change from baseline in the VRS for pruritus at Week 2.

### Patient Global Impression of Change (PGIC)

At the end of treatment (Day 15 or Early Termination Visit) subjects in Cohort 3 will be asked to rate their degree of improvement (or worsening) of their AD compared to before the start of treatment with study drug, using a 7-point scale. The scale ranges from 1 (very much approved) to 7 (very much worse).

The PGIC will be dichotomized into responders, defined as responses of 'Very Much Improved', 'Much Improved' or 'Minimally improved' (1, 2 or 3 on the scale above) and non-responders (4, 5, 6, or 7 on the scale above, plus missing data).

SAP Version v2.0 Page 18 of 43

Date: 16th March 2017

### **Body Surface Area (BSA)**

Assessment of the percentage of a subject's BSA affected by AD will be made by best estimates of the Investigator at each visit for subjects in Cohorts 2 and 3. Affected BSA must be  $\geq$  10% and  $\leq$ 40% at screening and must be  $\geq$  10% and  $\leq$ 50% on Day 1 for the patient to be randomised.

The endpoints associated with BSA for Cohort 3 are change from baseline and percentage change from baseline at Week 2.

### 4.3. EXPLORATORY ENDPOINT

#### **Ziarco Ointment Questionnaire**

This is assessed at the end of the treatment phase for each cohort. Subjects will be asked a series of questions about their impressions of the study ointment they have used. Information regarding the ointment will be used to learn the practicalities of handling the ointment in a clinical setting for subsequent cohorts and clinical development (refer to Protocol Appendix 13 – Ziarco Ointment Questionnaire for a full list of questions).

#### 4.4. SAFETY ENDPOINTS

The safety endpoints assessed for all 3 cohorts are:

- Adverse events
- Vital signs (blood pressure, pulse rate, and temperature) –change from baseline at each visit, maximum and minimum on-treatment measurement
- 12-lead Electrocardiograms (ECG) change from baseline at each visit and maximum ontreatment measurement
- Laboratory safety tests (chemistry, haematology, and urinalysis) change from baseline and percentage change from baseline

### **Modified Draize Score**

For Cohort 1 subjects only, local toleration will be assessed by the modified Draize score prior to application of study ointment and until discharge from the CRU. For each assessment the grading value for erythema and eschar formation, oedema formation and desquamation will be recorded and the total of the three gradings will also be recorded. Grading is on a 5-point scale from 0-4, where 0=none to 4=severe.

#### 4.5. PHARMACOKINETIC ENDPOINTS

Plasma ZPL-5212372 concentrations will be determined for all 3 cohorts. All concentration values will be reviewed prior to analysis and values that appear to be unexpectedly high due to potential contamination will be excluded and the reason(s) documented.

The safety review meeting for Cohort 1 data showed insufficient data to enable pharmacokinetic (PK) parameters to be calculated for Cohort 1, due to the very low and sporadic systemic exposure in a small number of subjects who had study ointment applied over 40% BSA.

SAP Version v2.0 Page 19 of 43

PK parameters will be derived for Cohort 2 for Days 1 and 7. The ZPL-5212372 pharmacokinetic parameters  $AUC_{\tau}$ ,  $AUC_{last}$  and  $t_{\frac{1}{2}}$  will be generated using non-compartmental methods.  $C_{max}$  and  $T_{max}$  will be determined directly from the data. The parameters are:

**Day 1:** 

AUC $_{\tau}$  The area under the serum concentration versus time curve, from time 0 to 12

hours, as calculated using the linear trapezoidal method when concentrations are increasing and the logarithmic trapezoidal method when concentrations

Date: 16th March 2017

are decreasing.

Cmax Maximum observed drug concentration.

 $T_{max}$  Time of the maximum serum concentration. If the maximum value occurs at

more than one time point,  $T_{\text{max}}$  is defined as the first time point with this value.

Day 7:

AUC $_{\tau}$  The area under the serum concentration versus time curve, from time 0 to 12

hours, as calculated using the linear trapezoidal method when concentrations are increasing and the logarithmic trapezoidal method when concentrations

are decreasing.

AUClast The area under the serum concentration versus time curve, from time 0 to last

available time point (48 hours), as calculated using the linear trapezoidal method when concentrations are increasing and the logarithmic trapezoidal

method when concentrations are decreasing.

Cmax Maximum observed drug concentration.

Tmax Time of the maximum serum concentration. If the maximum value occurs at

more than one time point,  $T_{max}$  is defined as the first time point with this value.

Kel Where possible, the apparent terminal elimination phase rate constant (kel) will

be calculated by linear regression of the log-linear plasma concentration-time curve. Only those time points judged to describe the terminal log-linear decline will be used in the regression. Values for this parameter will only be reported for an individual if a minimum of 3 measurable concentration-time-points during the log-linear portion of the terminal elimination phase,

excluding Cmax, are available

t½ Apparent first-order terminal elimination half-life will be calculated as ln2/kel

RAUC $\tau$  Accumulation ratio calculated as Day 7 AUC $\tau$  / Day 1 AUC $\tau$ 

RCmax Accumulation ratio calculated as Day 7 Cmax / Day 1 Cmax

SAP Version v2.0 Page 20 of 43

Date: 16th March 2017

### 5. ANALYSIS SETS

#### 5.1. SCREENED POPULATION

The screened population will include all subjects who signed the informed consent form and are screened for participation in this study. This population will only be used for the purposes of describing the subject disposition.

#### 5.2. RANDOMISED SET

The randomised set will include all randomised subjects. This population will only be used for the purposes of describing the subject disposition.

### 5.3. FULL ANALYSIS SET (FAS)

The FAS will include all randomised subjects who receive at least one application of investigational medical product (IMP). Subjects will be included in their randomised treatment group even if they receive the wrong IMP. This population will be used for the primary efficacy analysis and most other analyses for efficacy and exploratory endpoints.

### 5.4. PER PROTOCOL (PP) ANALYSIS SET

The PP analysis set is only applicable for Cohort 3. It will include all subjects in the FAS who have not violated any inclusion or exclusion criteria and/or deviated from the protocol, in a way that could influence their efficacy assessment. For example subjects will be excluded if they:

- have poor IMP compliance, for example deviated from BID application over the 14 days and/or jar returned without being used. The IMP compliance will be assessed by a clinical review of dosing data and protocol deviations
- receive the incorrect IMP

Subjects will be included in their 'as treated' treatment group. Note that this will be the same as the randomised treatment because receiving the wrong IMP is a major deviation.

Data listings, including protocol deviations (Section 5.6), will be provided to identify subjects to be excluded from the PP analysis set. Precise reasons for excluding subjects will be documented prior to locking the database.

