Study Ointment Application	
 
1. The volume of ointment applied to each subject may vary e.g. based on the condition of their skin, body size and gender.
 
2. Subjects will have the same volume of ointment applied throughout the duration of the study. Any changes to a subjects recommended volume of study ointment will be documented.
 
	
 
1. The minimum amount of study ointment to adequately and evenly cover the dosing area should be used for each subject.
 
2. The minimum volume of study ointment that can be applied for each application is approximately 0.25 mL per 2% BSA covered i.e. 1.25 mL ointment for 10% BSA coverage; 5 mL for 40% BSA coverage & 6.25 mL for 50% BSA coverage.
 
3. The maximum volume of study ointment that can be applied for each application is approximately 1 mL per 2% BSA covered i.e. 5 mL ointment for 10% BSA coverage; 20 mL for 40% BSA coverage & 25 mL for 50% BSA coverage.
 
4. For Cohorts 1 and 2 the minimum amount of study ointment should be used for the first application. If there is not enough ointment to cover the dosing area additional study ointment can be applied (up to the maximum 1 mL per 2% BSA).
 
5. For Cohort 3 the minimum amount of study ointment should be used for the first application in the CRU. If there is not enough ointment to cover the dosing area additional study ointment can be applied (up to the maximum 1 mL per 2% BSA).
 

Study Emollient Application	
 
1. Cohorts 2 and 3 only. Adaptable use of different methods of application for study ointment and study emollient
 
2. Cohort 3 only. Alternate emollients other than those defined as 'study emollients'
 
	
 
1. Use of study ointment before or after study emollient administration
 
2. Duration of time between study ointment and study emollient applications between 5 and 30 minutes.
 
3. Stop the use of study emollient on areas treated with study ointment.
 

	may be used.	
 
4. Stop the use of study emollient in the event of any hypersensitivity reactions caused by emollient.
 
5. Change the emollient used from 'study emollient' due to any potential or actual hypersensitivity reactions with the approval of the Ziarco CMO (Cohort 3 only).
 

--	--------------	--

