## 5.5 Dispensing

[REDACTED]

For Cohort 3 study medication will be supplied to the subject as:

- Randomisation Visit (Day 1): 4 glass jars containing either 1.0% (w/w) ZPL-5212372 ointment or matching placebo ointment, plus an additional glass jar containing 1.0% (w/w) ZPL-5212372 ointment or matching placebo ointment, to be used as spare medication, in the event of late visits or lost/damaged container, to ensure continuous dosing.
- On Visit 3 (Day 8): empty or partially used glass jars containing either 1.0% (w/w) ZPL-5212372 ointment or matching placebo ointment will be replaced as required to enable dosing till the end of the study based on the patients usage. If required the spare ointment supply will also be replaced as necessary.

Cohort 3 patients will be supplied with an adequate quantity (including some spares) of [REDACTED] and sealable plastic bags to store and return used [REDACTED] for disposal at the CRU. In addition, patients will be supplied with an adequate quantity of disposable gloves to allow carers to apply the study ointment onto hard to reach areas of their body as required.

Cohort 3 patients will be instructed by the unit staff to only open and use one jar of study ointment at a time.

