#### 10.2. EXTENT OF EXPOSURE

For Cohorts 1 and 2, the number of days on treatment, the average daily volume administered and average daily amount of ointment used (based on a density of 1.1089 g/mL) will be summarised using descriptive statistics by treatment group for the FAS. The average daily volume administered and average daily amount of ointment used will be split by BSA treated within a cohort.

- Days on treatment = date of last dose date of first dose +1
- Daily volume administered = Total volume administered / number of days on treatment
- Daily amount of ointment used = daily volume administered \* density

SAP Version v2.0 Page 32 of 43

Date: 16th March 2017

For Cohort 3 the number of days on treatment and daily amount of ointment used will be summarised using descriptive statistics by treatment group for the FAS.

Daily amount of ointment used = (total weight of dispensed jars – total weight of returned jars) / days on treatment

If a jar is not returned then it will be assumed that the weight for this jar is missing and no daily amount of ointment used will be calculated for the subject.

Study drug administration, including all the variables specified above, will be listed.

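### SAP 5.4 gives an unopened returned jar as an example of poor compliance, but the Cohort 3 supply plan makes one the expected result of full compliance for many permitted treated areas and volumes

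*SAP*

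**What the plan says.** SAP 5.4 defines the PP set for Cohort 3 as FAS subjects without violations or deviations that could influence their efficacy assessment. It then gives examples of who is excluded, among them subjects who "have poor IMP compliance, for example deviated from BID application over the 14 days and/or jar returned without being used". The and/or lets the jar limb stand alone. The same bullet continues: "The IMP compliance will be assessed by a clinical review of dosing data and protocol deviations". The section closes with: "Precise reasons for excluding subjects will be documented prior to locking the database".

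Protocol 5.5 describes the Day 1 supply as four jars, "plus an additional glass jar containing 1.0% (w/w) ZPL-5212372 ointment or matching placebo ointment, to be used as spare medication". The spare is for late visits or a lost or damaged container. On Day 8 empty or part-used jars, and if required the spare, are replaced according to the patient's usage. Patients are "instructed by the unit staff to only open and use one jar of study ointment at a time". Protocol 5.4 gives 100 g per jar. Protocol 5.7 and SAP 3.5 give a different count, three jars per subject.

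Protocol Table 2 sets the minimum volume per application at "approximately 0.25 mL per 2% BSA covered i.e. 1.25 mL ointment for 10% BSA coverage; 5 mL for 40% BSA coverage", and the maximum at four times that. Cohort 3 may have 10% to 50% BSA treated.

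Protocol 5.10 monitors compliance by recording empty jars, weighing part-used ones and reviewing the diary. It does not treat an unopened jar as non-compliance.

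**The concern.** The spare is a contingency item. If nothing goes wrong it ends the study sealed. Because only one jar is open at a time, any jar beyond the patient's need also stays sealed. An unopened jar can therefore reflect oversupply, a small treated area or a thin application just as well as missed doses.

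At stake is what the PP analysis measures. It is the first robustness check that SAP 8.1.1 names for the EASI result, in a cohort planned at 20 active and 10 placebo. If the jar limb is followed, PP membership depends partly on treated area, volume and supply. It can also fail in the other direction: a patient with a large treated area who missed many doses may still have opened every jar.

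The SAP's other amount measure does not fill the gap. SAP 10.2 has "Daily amount of ointment used = (total weight of dispensed jars – total weight of returned jars) / days on treatment", which is not scaled to treated area. It is an exposure summary and is not offered as a PP criterion.

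**Working it through.** **Inputs.** Volume per application: 0.25 to 1 mL per 2% BSA (Protocol Table 2). Treated BSA: 10% to 50% (Protocol Table 2). Applications: 2 per day × 14 days = 28, the last on the evening of Day 14. Jar: 100 g (Protocol 5.4). Density: 1.1089 g/mL (SAP 10.2, stated for Cohorts 1 and 2 and assumed here for Cohort 3). Also assumed: constant volume, no waste or residue.

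**The plan's own figures.** Volume = (BSA/2) × rate. At 10%, 40% and 50% BSA this gives 1.25, 5 and 6.25 mL at the minimum rate and 5, 20 and 25 mL at the maximum, exactly as Table 2 states.

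**Use over 14 days at full compliance.** Grams = volume × 28 × 1.1089 = volume × 31.049. Jars opened = grams/100, rounded up. Brackets show jars opened; unused of 5; unused of 3, all before any Day 8 resupply.

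| BSA | Minimum volume | Half of maximum | Maximum volume |
|---|---|---|---|
| 10% | 38.8 g (1; 4; 2) | 77.6 g (1; 4; 2) | 155.2 g (2; 3; 1) |
| 20% | 77.6 g (1; 4; 2) | 155.2 g (2; 3; 1) | 310.5 g (4; 1; 0) |
| 30% | 116.4 g (2; 3; 1) | 232.9 g (3; 2; 0) | 465.7 g (5; 0; 0) |
| 40% | 155.2 g (2; 3; 1) | 310.5 g (4; 1; 0) | 621.0 g (7; 0; 0) |
| 50% | 194.1 g (2; 3; 1) | 388.1 g (4; 1; 0) | 776.2 g (8; 0; 0) |

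**Thresholds.**
- The fifth jar is opened once use passes 400 g: 400/31.049 = 12.88 mL per application. At the maximum rate that is 2 × 12.88 = 25.8% BSA. At half the maximum it is 51.5% and at the minimum 103%, both beyond the 50% limit.
- Five jars run out at 500 g: 500/31.049 = 16.10 mL, or 32.2% BSA at the maximum rate.
- Under the three-jar text, the third jar is opened past 200 g: 200/31.049 = 6.44 mL, or 12.9% BSA at the maximum rate and 51.5% at the minimum.

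**Density check.** At 1.0 g/mL, 50% BSA uses 175 g at the minimum volume (still two jars) and 700 g at the maximum (still more than five).

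**The opposite error.** At 50% BSA and maximum volume, just over 400 g of the expected 776.2 g opens all five Day 1 jars. Since 400/776.2 = 0.515, a patient who used little more than half the expected amount would pass the jar limb, although the missed-application limb could still catch them.

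**Grams per day.** 10% BSA at maximum: 2 × 5 × 1.1089 = 11.09 g/day. 40% BSA at minimum: 2 × 5 × 1.1089 = 11.09 g/day. The same figure is the permitted ceiling for one patient and the floor for another.

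**The case against.** A reader might infer that every Cohort 3 patient holds far more ointment than a compliant patient can use. The documents do not support that. Above about 32% BSA at the maximum volume, five jars are not enough and Day 8 replacement is needed. The minimum volume is a lower bound and the first-application starting amount, to be increased if coverage is inadequate. No distribution of treated BSA or volume is given.

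A reader might also infer that the SAP automatically excludes anyone with an unopened jar. It does not. The jar phrase is an example within an example, the deviation must be one that could influence the efficacy assessment, and clinical review decides before lock. Protocol 5.5 labels the fifth jar a spare, so reviewers would have a documented reason to discount it. Under the three-jar text the problem is smaller: at the maximum volume no Day 1 jar is left unopened above about 13% BSA.

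These points limit the claim but do not remove it. Reviewers are told that an unused jar indicates poor compliance, with no exemption for spare or surplus jars and no amount threshold. Protocol 5.7 says the Cohort 3 diary information will not be databased, so returned-jar data may carry much of the weight. Even with three jars, every compliant minimum-volume patient returns at least one unopened.

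**Conclusion.** The point holds as a conflict between a stated PP example and the supply plan. For many permitted combinations of area and volume, an unopened jar is what full compliance produces. Followed as written, the example would remove compliant patients, mainly those with small treated areas or low volumes.

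The reach is limited. PP is one of four sensitivity analyses in SAP 8.1.1, and Protocol 8.5.1 makes it optional. The primary analysis uses the FAS and is unaffected, so an inference that the primary result is compromised would be wrong. How many patients would be lost, or in which arm, cannot be computed from the documents.

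The figures rest on full 100 g jars, no waste, constant volume, 28 applications, the Cohort 1 and 2 density, and Day 1 supply only. The core result survives either jar count and a density of 1.0.

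**What to change.** 1. Delete the unused-jar example from SAP 5.4.
2. Define amount compliance as grams used (dispensed minus returned weight) divided by grams expected (recommended mL per application on the body map × 1.1089 × 2 × days on treatment). Fix the acceptable ratio before unblinding.
3. State that patients with an unreturned jar, for whom SAP 10.2 already calculates no usage, are judged on dosing records and protocol deviations alone.
4. Reconcile the jar counts in Protocol 5.5, Protocol 5.7 and SAP 3.5.

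Restricting the jar limb to patients who return every jar unopened would not work as a compromise. Protocol 5.9 takes the first clinic dose from one of the patient's own jars, so no patient dosed as planned could meet it.

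The cost is SAP wording and one derived variable. Jar weights and the body-map amount are already recorded under the protocol, so no new collection should be needed. The downside is that patients with an unreturned jar have no ratio.
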